Aim 2. Evaluate the preliminary efficacy of ACTivate in improving physical function and other outcomes in HCT patients (NIH Stage IB). As standard of care, all HCT patients undergo comprehensive functional evaluation (physical, cognitive, mental health, nutrition, social/financial, global, and quality of life) between sign-off (~10 days before HCT) and year 3. This will allow us to compare outcomes in the nine patients in Aim 1 plus an expansion cohort of 11 patients receiving the final iteration of ACTivate (total n=20) to contemporaneous controls matched for age, gender, and disease.

H1: Patients receiving ACTivate will have a shorter hospital stay and better physical function (six-minute walk, primary endpoint) at year 3.

3. **Background and Significance**

Allogeneic hematopoietic stem cell transplant (HCT) has the potential to cure patients with hematologic malignancies and other diseases, but treatment is arduous and there is significant risk of treatment-related morbidity and mortality. Worse clinical outcomes are predicted not only by advanced chronological age, but also by modifiable behavioral factors such as decreased physical function and comorbid psychological conditions, such as depression. Targeted interventions to reduce physical and psychological vulnerabilities during the pre-HCT time period could therefore improve treatment tolerance and HCT outcomes.

ACT [1] is a transdiagnostic, mindfulness-based treatment that has been effective in reducing psychological distress and symptom interference in a variety of clinical populations [2-5], including individuals with cancer [6-15]. Unlike more traditional cognitive-behavioral therapy (CBT), which focuses on changing thoughts/feelings themselves, ACT emphasizes psychological acceptance: voluntarily adopting an open, receptive posture with respect to moment-to-moment experience. This may be well-matched to individuals with cancer for whom distressing thoughts/feelings may not be illogical or irrational, but rather perfectly normal or expected responses to having a life-threatening illness (and embarking on a journey that could cure their disease but could also cause death), or simply inevitable during the course of treatment.

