Measures. Measures are outlined in Table 1. The majority of the assessments are collected as part of routine HCT procedures or tracked in the Duke Adult Bone Marrow Transplant (ABMT) database. Assessments that are not typically collected during HCT procedures have been marked with an (*). Primary outcomes will be the 6-minute walk and length of hospital stay. Target engagement (process of change) will be assessed with the Valuing Questionnaire (VQ) (or equivalent), administered to the patient and the caregiver every 2 weeks for the first 30 days, and once a month thereafter.

ACTivate sessions will be conducted in person or via the Duke extended care platform used for telehealth visits. Participants will also receive reminders of concepts from sessions and reinforcement or prompting from the study team via the custom HCT app (e.g., “Great job completing your steps yesterday!”). All sessions will be audio taped for fidelity review. Fidelity will be assessed with the ACT Measure (ACT-FM), along with an ACTivate protocol checklist (developed after finalization of the protocol in Aim 1). Session tapes from the second interventionist will be reviewed by [name] for ongoing training/consultation to maintain fidelity to the intervention.

Participants’ functional outcomes at Day 30 and Day 90 will be compared to age, gender, and disease-matched controls (case-control design), collected as standard of care.

Use of previously collected data: If a subject is simultaneously on another study and the same assessment or sample is required for both studies, we will only collect once and share the data between studies to avoid subjects having to duplicate efforts.

5. Selection of Subjects

Protocol Summary of: Pro00105683

Eligibility criteria: (1) Over the age of 18 (2) undergoing allogeneic HCT for any cancer or non-cancer illness, (3) English-speaking (4) has a caregiver who is willing to participate. Caregiver eligibility criteria: (1) Over the age of 18 and (2) English-speaking.

6. Subject Recruitment and Compensation

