Potential participants will be recruited from the Duke ABMT Program. Patients may learn about the study at the end of their new patient class, where the presenter will give the option for patients to stay after class and view a slideshow that briefly introduces the study. Under the current standard of care practice, ABMT physicians evaluate all new patients. If the patient's ABMT physician deems the patient to be an allogeneic transplant candidate and he/she meets basic eligibility criteria, the patient will be informed about the study. If the patient expresses interest in participating, they will be referred to research staff, who will review inclusion/exclusion criteria and tell the patient more about the study. Our target *N* is 20, and we anticipate achieving this target by recruiting 24 patients and caregivers. All recruited participants will be assigned to the intervention group, consistent with our use of a historical control group.

Participants will not receive direct compensation for participation in the study.

7. Consent Process

The ABMT physician and the research staff will make clear that participation in this research is voluntary, and patients may decline to hear more or to participate in the study without penalty; these patients will receive standard of care. Patients who are interested in learning more about the study will speak with study staff who will explain details, answer questions, and confirm inclusion/exclusion criteria. Caregivers will be identified by the HCT patient as a primary caregiver. They will be approached by study staff who will explain details, answer questions, and confirm inclusion/exclusion criteria. Patients and their caregivers will review the consent form with study staff in-person or over the phone. Potential participants will have ample time to ask questions and have those questions answered and consider whether they would like to participate. Only those who voluntarily provide full informed consent will proceed to study enrollment. Individuals who are screened but do not want to participate (do not give informed consent) will not be recorded and will receive standard care.

Subject's Capacity to Give Legally Effective Consent

We will exclude from participation anyone who does not have the capacity to give legal consent.

8. Study Interventions

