Relationship of Risks to Benefits: This is a low risk intervention study that does not involve the use of a study drug or investigational device. No adverse health effects had been established from the use of the iPhone or Apple Watch. There is risk of loss of confidentiality, as with any study, and with studies with mobile devices. Treatment-related morbidity is high among HCT patients and mortality ranges from 10-30%. The potential benefit of interventions to increase treatment tolerance is thus substantial. Given the minimal risks associated with the study methods, the risk-benefit analysis is highly favorable.

10. Costs to the Subject

There are no direct costs to subjects.

11. Data Analysis & Statistical Considerations

Study variables will be described using summary statistics and graphical methods. Continuous variables (e.g., 6 minute walk (primary endpoint), AAQ2) will use the generalized linear model with the outcome of interest at year 3 as the dependent variable and treatment assignment as the primary predictor of interest, with a priori selected covariates age, gender, and disease. Ordered categorical outcomes (e.g. Fried Frailty) will use ordered logistic regression models in the same form above. Other outcomes (e.g., length of stay) will be assessed using an adaptation of the Cox regression model [35]. Primary analyses will be followed by examining the extent to which engagement is associated with outcomes using appropriate modeling. We also will explore the trajectory of outcome changes using generalized linear repeated measures models. We will carefully examine model assumptions (e.g., residuals, linearity, influential cases) and reparameterize models accordingly. Assuming an alpha of 0.05 and 10% attrition at 90 days, for the continuous outcomes, a sample size of 60 (20:40) will afford 80% power to detect a standardized group difference of just over 0.8 SDs. This translates to about a 16 meter treatment group difference in the six minute walk test.

12. Data & Safety monitoring

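### Aim 2 calls the only efficacy comparator contemporaneous and Section 6 calls it historical; if it is historical, the stated matching and walk model leave calendar time confounded with treatment

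*Combined protocol and SAP*

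**What the plan says.** Section 2, Aim 2 compares the 20 patients given ACTivate "to contemporaneous controls matched for age, gender, and disease". Section 6 explains why nobody is assigned to a control arm: "All recruited participants will be assigned to the intervention group, consistent with our use of a historical control group".

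The Measures text in Section 4 says that functional "outcomes at Day 30 and Day 90 will be compared to age, gender, and disease-matched controls (case-control design), collected as standard of care". That gives the source of the control data and the matching factors, but no dates. Section 3 calls the design a pilot case-control study, and Section 8 confirms that everyone recruited is treated.

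Section 11 models continuous outcomes, including the six-minute walk, "with the outcome of interest at year 3 as the dependent variable", with treatment as the main predictor and "with a priori selected covariates age, gender, and disease". The sample size is 60, split 20 treated to 40 controls, with alpha 0.05, 10% attrition at 90 days and 80% power for a difference slightly above 0.8 SD, given as about 16 m on the walk.

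**The concern.** The two labels are instructions for choosing different patients. An analyst following Aim 2 would draw controls transplanted during accrual. An analyst following Section 6 would draw patients transplanted before it. Each would be following the protocol, and their estimates could differ.

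What is at stake depends on which label holds. With historical controls, treatment group and transplant era move together, and neither the matching nor the walk model contains a term for transplant date. A change over time in supportive care or case mix could then look like a benefit of ACTivate or hide one. With contemporaneous controls, the word is itself a restriction on calendar time, though an undated one, and most of this risk goes away. No other efficacy comparator is described, so H1 has nothing else to rest on.

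**Working it through.** **1. The statements side by side.**

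| Place | Control label | Dates | Factors used |
|---|---|---|---|
| Section 2, Aim 2 | contemporaneous | none | age, gender, disease |
| Section 4, Measures | matched, from standard-of-care data | none | age, gender, disease |
| Section 6 | historical | none | none stated |
| Section 11, walk model | no label | none | age, gender, disease |

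Nothing in the readable text reconciles the first and third rows. Section 11 does not list covariates for the length-of-stay analysis, so the statement about covariates is limited to the walk model.

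**2. The plan's own figure.** Inputs from Section 11: 20:40, 10% attrition, alpha 0.05 (taken as two-sided, since sidedness is not stated), 80% power. Evaluable: 20 × 0.9 = 18 and 40 × 0.9 = 36.

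- SE of the standardised difference = √(1/18 + 1/36) = √0.0833 = 0.289.
- Normal approximation: (1.960 + 0.842) × 0.289 = 0.809 SD.
- Noncentral t, 52 df: 0.824 SD.

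Both agree with the plan. The calculation makes no allowance for a difference between eras. The SD implied by the plan is about 16/0.8 = 20 m.

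**3. What an unadjusted shift would do.** The documents give no size or direction for drift, so every shift below is an assumption. The rejection probability is that of a noncentral t with 52 df and noncentrality shift/0.289; for 0.2 SD this is 0.2/0.289 = 0.69. The last column takes a true effect of 0.824 SD with the shift working against it.

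| Assumed net shift | In metres at SD 20 | Two-sided rejection, no true effect | Power, adverse shift |
|---|---|---|---|
| 0 | 0 | 5.0% | 80% |
| 0.1 SD | 2 | 6.3% | 69% |
| 0.2 SD | 4 | 10.4% | 56% |
| 0.3 SD | 6 | 17.5% | 43% |
| 0.5 SD | 10 | 39.8% | 20% |

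These use day-90 numbers, whereas the walk model is at year 3, for which evaluable numbers are not given. If 30% were lost (an assumption, set at the top of the 10-30% mortality range in Section 3), 14:28 would remain and a 0.2 SD shift would give 9.2%. That is lower because precision is lower, not because the bias is smaller.

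**4. Cost of adjusting for transplant year.** Assume a 2-year accrual, uniform transplant dates and one third treated. The variance inflation for the treatment effect is (between + within)/within, where between and within are the components of variance of transplant date.

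- Controls from the same 2 years: between = 0, inflation 1.00, detectable difference 0.82 SD.
- Controls from 3 years before accrual through its end: mean dates are 1.0 and −0.5, so between = (1/3)(2/3)(1.5²) = 0.50. Within = (1/3)(4/12) + (2/3)(25/12) = 1.50. Inflation 2.00/1.50 = 1.33, SE × 1.15, detectable 0.95 SD.
- Controls only from the 3 years before accrual: between = (2/9)(2.5²) = 1.389, within = (1/3)(4/12) + (2/3)(9/12) = 0.611. Inflation 2.00/0.611 = 3.27, SE × 1.81, detectable 1.49 SD. Here the adjustment also relies on extrapolating a trend.

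These figures leave out the planned covariates.

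**The case against.** The strongest reply is that Aim 2 defines the comparison, while the Section 6 phrase is a subordinate clause about recruitment. There, historical may loosely mean taken from records rather than enrolled, which would fit the Section 4 description. This is possible, but no text says so, and the ordinary meaning of the word points to an earlier period. The reply limits how much can be concluded; it does not remove the need to reconcile the two sentences.

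It is also fair that this is a Stage IB pilot of preliminary efficacy, in which matching on a few factors is defensible. That stands. A pilot that states a hypothesis and a power calculation still needs one control group.

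A reader might infer more than the documents support:

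- *That the trial is confounded by era.* This follows only under the Section 6 label.
- *That the plan has no control window at all.* Figure 2, the timeline, is not shown, so absence can be claimed only for the readable text. A date in that figure would not cure the conflict of labels.
- *That drift of a particular size is present.* No document shows any. The larger shifts in the table need strong trends: with mean transplant dates 2.5 years apart, 0.5 SD means 0.2 SD per year.
- *That the control group is also shown to be biased by selection.* Treated patients must speak English and each "has a caregiver who is willing to participate", and no text applies this to controls. Nor does any text show that either factor predicts outcome. People who decline "will not be recorded and will receive standard care", so some could be among concurrent controls, again with unknown effect. The lack of a named matching algorithm is likewise missing detail rather than an error.

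**Conclusion.** The contradiction is real and sits in current text. It affects what the only efficacy comparison can show, so the protocol should be corrected. Confounding by calendar time is conditional: it arises if controls are historical and is much smaller if they are contemporaneous.

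The conclusion rests on the wording, not on the illustration. The rise from 5% to 10.4% assumes a net 0.2 SD shift, 18:36 evaluable, a two-sided test and no true effect. The documents establish neither the existence nor the direction of such a shift. The plan's stated power is reproduced and is not in dispute.

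**What to change.** 1. Reconcile Section 2 (Aim 2) and Section 6 into one definition, for example: *Controls will be adult allogeneic HCT recipients at this centre who did not receive ACTivate, transplanted between [date] and [date], selected 2:1 on age, gender and disease. The list will be fixed before control outcomes are extracted.* Use the accrual window where it yields enough matches.
2. If the control and accrual windows differ but overlap, add transplant year as a matching factor or covariate and accept the loss of precision (SE about × 1.15 under the assumed window above). If they do not overlap, state that era cannot be separated from treatment except by extrapolating a trend, and word the H1 conclusion accordingly.
3. Add baseline six-minute walk as a covariate in the Section 11 walk model. Table 1 does not mark it as outside routine care, so it should exist for controls, and Section 4 places the treated baseline before the first session. State its timing in each group: standard evaluation starts at sign-off, about 10 days before HCT (Section 2), while treated patients are recruited around workup (Section 4). This addresses baseline imbalance and precision, not era.

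The cost is protocol wording and some chart work, with no new visits. A narrower window means a smaller pool of matches. Concurrent controls may also be exposed to the care team's orientation to ACTivate (Section 3), which would tend to pull the estimate towards no difference. Historical controls avoid that exposure but bring back the era problem.

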Significance. The curative potential of HCT is balanced by the significant risk of treatment-related morbidity, and mortality ranges from 10-30% [23-25]. Outcomes are worse in patients of advanced age, decreased physical function, and depressed mood [26-29]. Targeted interventions that reduce physical and psychological vulnerabilities pre-HCT have the potential to increase treatment tolerance and dramatically change illness trajectories and maintain long-term mobility and quality of life post-HCT, particularly for older adults. ACT is a newer CBT that has significant potential for this purpose [4]. ACT has decreased psychological distress and symptom interference and produced behavior change in a variety of clinical populations, including individuals with depression, anxiety, disordered eating, diabetes, and chronic pain [2-5]. Unlike traditional CBT, which focuses on correcting cognitive distortions, the target mechanism in ACT is psychological flexibility (the ability to allow experience to be what it is and move in the direction of values) [16]. Increased psychological flexibility may help HCT patients accept their situation (and the distressing thoughts/feelings that arise) and direct their attention to how they want to live the moments of their lives and to the things they can control.

For example, chemotherapy/radiation creates adverse interoceptive signaling (nausea, pain, fatigue) that may elicit maladaptive behavioral response patterns in HCT patients (sedentary behavior, disengagement, suboptimal nutritional intake). Individuals must actively choose to override these signals and engage in behaviors that may briefly intensify uncomfortable experiences in the service of improving treatment outcomes (walking, drinking protein shakes). Through ACT, individuals may better accept the discomfort associated with HCT and adapt behaviors in ways that improve function and survival. Further, the infusion of personal values in ACT may increase patient motivation to engage in health behaviors, even in the face of uncertain outcomes.

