We will recruit 20 adults around HCT workup (when patients undergo medical testing and commit to HCT). To be eligible, participants must be ≥ 18 years old ($n=10 < 60$ years, $n=10 \geq 60$ years), English speaking and receiving allogeneic HCT. They must also have a caregiver who is willing to participate. This age range is selected because the Duke Adult Blood and Marrow Transplant Program only cares for adults ≥ 18 years, and because we want to evaluate the impact in older and younger patients, we plan to recruit 10 < 60 years and 10 ≥ 60 years. Patients and their caregivers will complete a 1-6 session ACT protocol tailored to the clinical challenges of HCT. Assessments (outlined in Table 1) will be administered at key points to assess target engagement (process of change) and treatment outcomes. Self-report measures will be administered via a secure online survey tool (REDCap). Please see appendix A for REDCap survey distribution details. The caregiver will participate in the baseline and exit interviews, complete the acceptability measures, psychological assessments (with themselves as the identified person), and stool and skin collection. All other measures will only be completed by the patient. Patients will also use a custom HCT mobile application (or app) -- either Technology Recordings to better Understand BMT (TRU-BMT) (used in our previous studies (Pro00068979 and Pro00092963)) or SplendoFit -- to report things such as symptoms, diet and exercise, and wear an activity tracker (Apple Watch) during the intervention. Step data will be passively transmitted to the treatment team daily from the Apple Watch. We do not expect that there will be technical difficulty with the use of TRU-BMT or SplendoFit apps. The TRU-BMT app has already been piloted in Duke HCT patients (Pro00068979, PI [name], co-I [name]) and was rated favorably as both easy to use and helpful (abstract presentation at the American Society of Hematology 2017 Annual Meeting).

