In rare circumstances, and with the permission of the principle investigators, subjects may be allowed to use their personal activity tracking devices (such as an Apple Watch or FitBit) to track activity metrics such as step count. The activity tracking data from a subject's personal device will be shared with only key personnel on this study and with the subject's permission as outlined in the informed consent form. If subjects are allowed to use their personal activity tracker, we will only export activity data from their devices (such as a csv file) and will not be downloading the TRU-BMT or SplendoFit app on their personal device. Rare circumstances may include that subjects refuse to use the Duke provided Apple Watch and they have their own activity trackers.

Protocol Summary of: Pro00105683

Participants will complete informed consent procedures before the baseline assessment. Following the baseline assessment, patients and their caregivers will complete the first ACTivate session, and treatment will continue as outlined in Figure 2. ACTivate sessions will be audio recorded for training purposes to allow [name] to train others on how to conduct ACTivate sessions. Participants will be made aware that their sessions will be audio recorded at the time of informed consent procedures. Audio files will be recorded using a Duke encrypted Olympus DS Digital Voice Recorder on loan through the Duke Research Navigators program or using the Audacity software (Duke IRB approved) on an encrypted and password-protected Duke computer. The Olympus DS Digital Voice Recorder is password protected and has DSS Pro real-time 256-bit file encryption. Audio files will be saved to the project's secure folder behind the Duke server. Only IRB-approved key personnel will have access to the recorder and the audio recordings.

During Aim 1, we will make rapid iterations of the protocol after each cohort of $n=3$ to maximize acceptability and effectiveness (Stage 1A). All intervention will be conducted by [name] (a licensed psychologist with ACT expertise). For Aim 2, a second interventionist will be trained in the protocol, and we will continue to enroll patients in the final iteration of ACTivate until reaching 20 patients total (Stage 1B).

ACT Session Schedule

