Table 1. Assessments	Baseline	Every 2 Weeks	Continuous from Baseline	Day 30, Day 90, Day 180, Year 1, Year 2, Year 3
Physical function				
6-minute walk	X			X
Short physical performance battery	X			X
30 second sit-stand	X			X

Protocol Summary of: Pro00105683

Step count (activity tracker data)			X	
Falls question	X			X
PROMIS Fatigue*	X			X
PROMIS Physical Function*	X			X
Cognitive function				
Montreal Cognitive Assessment	X			X
PROMIS Cognitive Function*	X			X
Emotional / Psychological				
PHQ-9 (Depression)**	X			X
Valuing Questionnaire (VQ)*	X	X		
PC-PTSD/PCL**	X			X
PROMIS Depression**	X			X
PROMIS Anxiety**	X			X
PROMIS Emotional Support**	X			X
PROMIS Social Isolation**	X			X
HHI-12*	X			X
Brief COPE*	X			X
AAQ-II*	X			X
Nutrition				
Albumin	X			X
Body-mass index			X	
PONS	X			X
Clinician SGA	X			X
PG-SGA*	X			X
ASA-24*	X			X
Social/financial				
CMS Social determinants of health	X			X
FACIT-COST	X			X
Sociodemographics**	X			
SES (caregiver only)*	X			X (only Day 180, year 1, 2, 3)
Financial Assessment	X			X
Global				
Fried Frailty	X			X
OARS IADLs	X			X
Quality of life				
FACT BMT	X			X
FACT GP (caregiver only)*	X			X
EQ-5D-5L	X			X
Lorig Self Efficacy *	X			X
Self-Efficacy Preparedness for Caregivers (caregiver only)*	X			X
Miscellaneous				
PROMIS Global Health*	X			X

Protocol Summary of: Pro00105683

PROMIS Sleep*	X			X
HCT-CI (completed by MD)	X			
Clinical outcomes				
Adverse events (e.g., graft-host disease)			X	
Resource utilization (e.g., length of hospital stay)			X	
Symptoms				
PRO-CTCAE core symptoms*	Weekly through year 1			
Sample collections				
Stool**	X			X + Day 0, 7, 14, 21, 60
Skin**	X			X
Blood*	X			X + Day 14
Treatment development				
Acceptability survey**	X			X (only during ACT session time points as listed above)
Exit Interviews**				X
Note: Measures not collected as part of routine care are marked with an *. Measures marked with ** are assessments taken by caregivers too. All year 3 biosample collections will be optional.				

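### The primary model for the year-3 six-minute walk adjusts only for the matching factors and leaves out the baseline walk, in a comparison that is not randomised.

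*Combined protocol and SAP*

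**What the plan says.** Section 11 takes the outcome at year 3 as the dependent variable, labels the six-minute walk the primary endpoint, and names "treatment assignment as the primary predictor of interest, with a priori selected covariates age, gender, and disease". It names no baseline walk, change score or other baseline measure of function. Repeated-measures models of trajectories are also planned, but as exploration and without stated covariates.

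Aim 2 (Section 2) compares 20 ACTivate patients with "contemporaneous controls matched for age, gender, and disease". Section 6 assigns everyone recruited to the intervention. Section 5 requires that each patient "has a caregiver who is willing to participate"; no such condition is stated for controls.

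Three further places bear on whether a baseline walk matters and is available:

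- Section 3 says: "Outcomes are worse in patients of advanced age, decreased physical function, and depressed mood".
- Aim 2 says that, as standard of care, "all HCT patients undergo comprehensive functional evaluation (physical, cognitive, mental health, nutrition, social/financial, global, and quality of life) between sign-off" (about 10 days before transplant) and year 3.
- Table 1 schedules the six-minute walk at baseline with no asterisk, and its note explains: "Measures not collected as part of routine care are marked with an" asterisk. The baseline walk is therefore routine care.

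On timing, Section 4 says "We will recruit 20 adults around HCT workup" and "Following the baseline assessment, patients and their caregivers will complete the first ACTivate session".

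**The concern.** Matching on age, gender and disease and then adjusting for the same three factors adds little control of confounding beyond the matching. A patient's walking capacity before transplant can differ widely within a stratum of those factors, and nothing in the primary model accounts for it.

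In a randomised trial this would mainly cost precision. Here it can also bias the estimate. Treated patients are volunteers with a committed caregiver, while controls are drawn from standard-of-care records. The documents do not show which group is fitter, so a difference could create an apparent ACTivate effect or hide a real one. The omitted variable is the same test as the endpoint, and the protocol itself counts poor physical function as a predictor of worse outcome.

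**Working it through.** **Inputs from Section 11.** Sample size 60 (20:40), alpha 0.05, 80% power, 10% attrition at 90 days, detectable difference just over 0.8 SD, said to be about 16 m. The test's sidedness is not stated; I take it as two-sided.

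**Inputs assumed.** r is the correlation of baseline and year-3 walk given age, gender and disease: 0.2, 0.3, 0.5 or 0.7. δ is the baseline imbalance: 0.3 or 0.5 SD, in either direction. The documents give neither.

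**1. The plan's own figure.** After 10% attrition the groups are 18 and 36.

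- Normal approximation: (1.960 + 0.842) × √(1/18 + 1/36) = 2.802 × 0.2887 = 0.809 SD.
- Noncentral t: 0.824 SD.

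Both match just over 0.8 SD, so the plan's figure reproduces. It is the figure for an unadjusted two-group comparison, so no gain from a baseline covariate was counted. The implied scale is 16/0.824 = 19.4 m per SD.

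**2. Precision.** With balanced baselines, adjustment multiplies the residual SD by √(1 − r²), which is worth a sample-size factor of 1/(1 − r²). The 14:28 column assumes 30% loss by year 3, because the plan's 10% refers to 90 days.

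| r | Detectable, 18:36 | Power at 0.824 SD, 18:36 | Detectable, 14:28 | Sample-size factor |
|---|---|---|---|---|
| none | 0.824 SD | 0.80 | 0.940 SD | 1.00 |
| 0.2 | 0.807 | 0.816 | 0.921 | 1.04 |
| 0.3 | 0.786 | 0.835 | 0.897 | 1.10 |
| 0.5 | 0.714 | 0.899 | 0.814 | 1.33 |
| 0.7 | 0.589 | 0.975 | 0.671 | 1.96 |

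Imbalance gives back part of this gain. The standard error rises by √(1 + (2/9)δ²), which is 1.010 at δ = 0.3 and 1.027 at δ = 0.5. At r = 0.2 and δ = 0.5 the net factor is 0.980 × 1.027 = 1.007, so there is no gain.

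**3. Bias without the baseline walk.** Bias = r × δ. The rejection rate under no true effect comes from the noncentral t with that shift.

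| δ | r | Bias | False positives, 18:36 | False positives, 14:28 |
|---|---|---|---|---|
| 0.3 | 0.2 | 0.06 SD | 5.5% | 5.4% |
| 0.3 | 0.3 | 0.09 | 6.1% | 5.8% |
| 0.3 | 0.5 | 0.15 | 8.0% | 7.3% |
| 0.3 | 0.7 | 0.21 | 11.0% | 9.6% |
| 0.5 | 0.2 | 0.10 | 6.3% | 6.0% |
| 0.5 | 0.3 | 0.15 | 8.0% | 7.3% |
| 0.5 | 0.5 | 0.25 | 13.6% | 11.6% |
| 0.5 | 0.7 | 0.35 | 22.2% | 18.1% |

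On the plan's scale, 0.06 × 19.4 = 1.2 m and 0.35 × 19.4 = 6.8 m.

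**4. Does adjustment repair it?** In simulation at 18:36 (20,000 runs per setting) with baseline in the model, false positives were 4.8% to 5.2% and mean bias was within 0.005 SD of zero. The simulation assumes that baseline is measured without error and at the same time in both groups.

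**The case against.** The strongest reply is that the harm is assumed, not shown. The documents give no imbalance, direction or correlation. At an imbalance of 0.1 to 0.2 SD the false-positive rate is only 5.1% to 7.6%. The 22% figure needs the worst corner of the range: if age, gender and disease explain 20% of both walks and all of it is shared (an assumption), a partial r of 0.7 means a raw correlation of 0.2 + 0.8 × 0.7 = 0.76 across a transplant and three years. A raw correlation of 0.5 is then a partial r of 0.375, giving 6.7% (δ = 0.3) and 9.8% (δ = 0.5) at 18:36. All of this stands, and it is why the size is stated as a range.

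The metre conversion is approximate: bias is in SDs conditional on the covariates, whereas 19.4 m comes from an unadjusted calculation. Under the same 20% assumption the range becomes about 1.0 to 6.1 m.

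The covariate is not risk-free. Recruitment is around workup, routine evaluation starts at sign-off, and ACTivate aims to change exercise before transplant. A sign-off walk in a treated patient might already reflect the intervention. Measurement error would also leave some bias: with an assumed reliability of 0.8, about 20% remains. These points stand and shape the fix.

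It can also be said that this is a pilot, that the trajectory models may use baseline, and that Section 4 names length of stay as a second primary outcome and places the functional comparison at Day 30 and Day 90. None of these removes the gap. The trajectory models are exploratory, Aim 2 and Section 11 both name the year-3 walk as the primary endpoint, and the omission would matter at any time point.

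**Conclusion.** The concern holds. The primary walk model omits the one baseline variable most directly tied to its endpoint, in a design where randomisation cannot be relied on to balance it, and no confirmatory analysis elsewhere repairs this.

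How much it matters depends on two unknowns. If r is 0.2 to 0.3, both the bias and the lost precision are small. If r is 0.5 or more and the groups differ by 0.3 to 0.5 SD, the bias is 0.15 to 0.35 SD and false positives run from 8% to 22% at 18:36, or 7% to 18% at 14:28. Direction is unknown. The change should be made, because it is cheap and far more credible when specified before outcomes are seen. Confidence is medium, since r, the imbalance and the timing of control baselines are not documented.

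**What to change.** In Section 11, add the baseline six-minute walk as a pre-specified covariate in the primary model, beside age, gender and disease. Around that sentence:

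- Define baseline as a walk taken before session 1 in ACTivate patients and, in controls, a pre-transplant walk at as similar a time as possible.
- Before finalising, confirm from the database that the selected controls have a dated baseline walk.
- Report baseline mean, SD, number missing and days before transplant by group.
- If timing differs, add a sensitivity analysis restricted to patients with overlapping timing.
- State in advance how missing baselines are handled.
- Do the same for other continuous or ordinal outcomes with a routine-care baseline. HCT-CI (Table 1) could be added in a sensitivity analysis only.

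The cost is one sentence, one database check, about one degree of freedom per model, and the loss or imputation of patients without a baseline walk (number unknown). If baseline timing differs between groups, the covariate can itself introduce bias, so the timing check is a condition of using it. Confounding by unmeasured factors such as motivation would remain and should be acknowledged.
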